#### **5.1.1. Procedures for Breaking Treatment Codes**

In the event of a medical emergency where breaking the blind is required to provide medical care to the subject, the investigator (or designee) may obtain treatment assignment directly from the IWRS system for that subject (refer to Study Reference Binder for IWRS unblinding instructions). Gilead recommends but does not require that the investigator contact the Gilead medical monitor before breaking the blind. Treatment assignment should remain blinded unless that knowledge is necessary to determine subject emergency medical care. The rationale for unblinding must be clearly explained in source documentation and on the electronic case report form (eCRF), along with the date on which the treatment assignment was obtained. The investigator is requested to contact the Gilead medical monitor promptly in case of any treatment unblinding.

Blinding of study treatment is critical to the integrity of this clinical trial and therefore, if a subject's treatment assignment is disclosed to the investigator, the subject will have study treatment discontinued. All subjects will be followed until study completion unless consent to do so is specifically withdrawn by the subject.

Gilead Drug Safety and Public Health (DSPH) may independently unblind cases for expedited reporting of suspected unexpected serious adverse reactions (SUSARs).

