#### **6.5. Assessments for Premature Discontinuation from Study**

Subjects prematurely discontinuing from the study (for example, as a result of an AE), should have an Early Termination (ET) visit, if possible, and a Follow-Up visit 4 weeks after the date of last dose of study drugs. The study assessments to be performed at the ET visit are the same as those performed at the Week 12 visit (refer to Section 6.4.4). The study assessments to be performed at the Follow-Up visit are listed in Section 6.4.6. The subject will then be withdrawn from the study.

If these visits are not possible or acceptable to the subject or investigator, the subject may be withdrawn from the study.

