3.6. Missing Data and Outliers

3.6.1. Missing Data

In general, missing data will not be imputed unless methods for handling missing data are specified. Exceptions are presented in this document.

For missing MRI-PDFF, imputation rules are specified in Section 6.2.3. For missing last dosing date of study drug, imputation rules are described in Section 4.2.1. The handling of missing or incomplete dates for AE onset is described in Section 7.1.5.2, and for prior and concomitant medications in Section 7.4.

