3.8.2. Definition Analysis Visit Windows

Subject visits might not occur on protocol-specified days. Therefore, for the purpose of analysis, observations will be assigned to analysis windows.

In general, the baseline value will be the last nonmissing value on or prior to the first dosing date of study drug. For imaging the data, baseline will be the first nonmissing value from screening up to first dosing date plus 4 weeks.

Selected safety and efficacy data collected up to and including the last dosing date plus 30 days (or 42 days for imaging data) will be mapped according to the following analysis windows. Early termination (ET) or follow-up (FU) will use the nominal visit name.

Table 3-1. Analysis Visit Windows for Vital Signs Including Weight, Chemistry, Hematology, Coagulation Labs, Lipid Profile, and Pooled Cohort Score and Risk

Analysis Visit	Study Day	Lower Limit	Upper Limit
Baseline/Day	1	NA	1
Week 1	8	2	18
Week 4	29	19	42
Week 8	57	43	70
Week 12	85	71	> 85

NA = not applicable

Table 3-2. Analysis Visit Windows for FibroSure/FibroTest, CK-18, ELF (and its components), Free Fatty Acid, C-Reactive Protein, ApoA1, ApoB, and Bile Acids

Analysis Visit	Study Day	Lower Limit	Upper Limit
Baseline/Day	1	NA	1
Week 1	8	2	18
Week 4	29	19	56
Week 12	85	57	> 85

Table 3-3. Analysis Visit Windows for Insulin and HOMA-IR

Analysis Visit	Study Day	Lower Limit	Upper Limit
Baseline/Day	1	NA	1
Week 4	29	2	56
Week 12	85	57	> 85

Table 3-4. Analysis Visit Windows for Waist Circumference, ECG, HbA1c, and QoL-Questionnaire

Analysis Visit	Study Day	Lower Limit	Upper Limit
Baseline/Day	1	NA	1
Week 12	85	2	> 85

Table 3-5. Analysis Visit Windows for FibroScan, MRE, and MRI-PDFF

Analysis Visit	Study Day	Lower Limit	Upper Limit
Baseline/Day	1	NA	29
Week 12	85	30	> 85

Data relating to unscheduled visits may be assigned to a particular visit or time point. The following conventions will be followed:

- An unscheduled visit prior to the first dosing of study drug will be included in the calculation of the baseline value.
- For subjects who prematurely discontinue from the study, early termination (ET) data will be summarized as a separate visit, labeled as “Early Termination Visit”
- Data collected on a follow-up visit will be summarized as a separate visit, and labeled “Follow-up Visit.”

3.8.3. Selection of Data in the Event of Multiple Records in an Analysis Visit Window

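### SAP 3.8.2 keeps early-termination values out of Week 12 even when they were taken near Day 85, while non-ET records from as early as Day 2 or Day 30 can count as Week 12

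*SAP*

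**What the plan says.** SAP 3.8.2 places observations in date windows because visits may miss their planned day. ET records are exempt: "Early termination (ET) or follow-up (FU) will use the nominal visit name". For subjects who leave the study early, "early termination (ET) data will be summarized as a separate visit".

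The Week 12 windows are all centred on Day 85 and have no fixed upper day, but they open at different days:

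- Table 3-1 (vital signs, safety laboratory tests, lipids): Day 71.
- Tables 3-2 and 3-3 (serum markers; insulin and HOMA-IR): Day 57.
- Table 3-4 ("Analysis Visit Windows for Waist Circumference, ECG, HbA1c, and QoL-Questionnaire"): Day 2.
- Table 3-5 (FibroScan, MRE, MRI-PDFF): Day 30.

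Unscheduled records may be assigned to a visit. For continuous data, SAP 3.8.3 takes the record nearest the nominal day.

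On missing data, SAP 3.6.1 imputes nothing unless a method is given, and adds: "For missing MRI-PDFF, imputation rules are specified in Section 6.2.3". That section only substitutes one MRI series (DDE) for another (ME).

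Protocol 6.5 and footnote b of Protocol Appendix 2 give early stoppers the Week 12 procedures, including MRE and MRI-PDFF, at an ET visit, followed by a Follow-Up visit. For those leaving the study, Protocol 6.5 then says: "The subject will then be withdrawn from the study".

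**The concern.** Whether a value enters Week 12 depends on the name of the visit, not on when the value was taken. The nearest-day rule cannot correct this, because an ET record is never a candidate for the Week 12 window.

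This matters for endpoints measured only at baseline and Week 12, where the ET value is usually the only on-study value of a subject who leaves early. Two readable analyses are exposed. SAP 6.3 reports, by diabetes subgroup, the Week 12 proportions with at least 30% reduction in MRI-PDFF and at least 15% in MRE, together with ANCOVA of Week 12 change. It states neither a denominator nor a rule for subjects without a Week 12 scan. SAP 7.5 cross-tabulates baseline and Week 12 ECG assessments and takes subjects with a missing value out of the denominator. A subject who stops because of an adverse event may thus have an ET ECG that this table does not use.

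Protocol 1.3.1 singles out the 30% MRI-PDFF reduction as important, so its handling should be settled in advance.

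**Working it through.** **Step 1. Same window, different labels.** Protocol 6.4.4 allows the Week 12 visit 7 days either side, that is Days 78 to 92.

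| Record | Days before Day 85 | Week 12 value? |
|---|---|---|
| ET scan, Day 80 | 85 − 80 = 5 | No: keeps its ET label |
| Unscheduled scan, Day 30 | 85 − 30 = 55 | Can be (Table 3-5) |
| ET ECG or HbA1c, Day 80 | 5 | No |
| Unscheduled ECG or HbA1c, Day 2 | 85 − 2 = 83 | Can be (Table 3-4) |

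The Day 80 ET record lies within the visit tolerance and is left out. The two early records lie far outside it and are admissible when nothing nearer exists.

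**Step 2. Who has no Week 12 value.** Imaging is mapped up to 42 days after the last dose. A subject who stopped drug but still had a nominal Week 12 scan on Day 85 is therefore counted if the last dose was on or after Day 85 − 42 = Day 43. The 30-day limit for other data gives Day 85 − 30 = Day 55. Subjects who leave the study after an ET visit have no such scan. Since SAP 6.2.3 does not cover an absent scan, they are missing at Week 12 in the readable analyses.

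**Step 3. Effect on a response rate.** SAP 1.3 assumes 32% response in the 20 mg arm (N = 50), which is 0.32 × 50 = 16 responders. Let m subjects lack a Week 12 value, of whom s would have been responders. The observed-case rate is (16 − s)/(50 − m). The documents give no ET rate, so m is an assumption.

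| m | All m non-responders (s = 0) | All m responders (s = m) |
|---|---|---|
| 0 | 16/50 = 32.0% | 16/50 = 32.0% |
| 2 | 16/48 = 33.3% | 14/48 = 29.2% |
| 5 | 16/45 = 35.6% | 11/45 = 24.4% |
| 10 | 16/40 = 40.0% | 6/40 = 15.0% |

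For m = 5 the shift runs from +3.6 to −7.6 percentage points. It is zero only if the lost subjects respond at the same 32% as the rest.

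**Step 4. The plan's own figure.** SAP 1.3 states 80% power for 4% (N = 25) against 32% (N = 50) by two-sided Fisher's exact test. Exact enumeration with 0.025 in each tail gives 80.3%, so the figure reproduces. With the other common definition of the two-sided p-value it is 85.0%. Nothing in this point disputes it.

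**The case against.** **ET data are kept.** They are summarized as their own visit, and SAP 6.2.2 lists all exploratory efficacy endpoints. Keeping scans with shorter exposure apart from a 12-week endpoint is a defensible choice. This stands, but it does not explain why an ET scan on Day 80 is excluded while a non-ET scan on Day 30 is admissible.

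**The stray early reading is remote.** The schedule has no other on-treatment assessment of these parameters, and the minimum content of an unscheduled visit (Protocol 6.4.5) includes none of them. Unscheduled data only may be assigned, and for continuous data the nearest record wins. This also stands. The wide windows are a loose end more than a likely source of error. However, the nearest-day rule is written for continuous measurements, not for categorical ECG assessments.

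**Most of the primary safety analysis is untouched.** Treatment-emergent adverse events, graded laboratory abnormalities and liver-injury criteria use data to 30 days after last dose, whatever the visit label. The ECG shift table is the exception.

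**Not every early stopper leaves the study.** Protocol 5.1.1 says of subjects taken off drug after unblinding: "All subjects will be followed until study completion unless consent to do so is specifically withdrawn by the subject". Protocol 6.9 defines study completion regardless of treatment duration. Some who stop drug may therefore still have a nominal Week 12 visit.

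**Power.** A reader might infer a loss of power. The documents do not support a figure. They give no ET rate, disclaim formal power calculation and plan no formal testing. Inflated rates and lost power also do not go together. With 22 against 45 subjects and unchanged rates, the calculation of Step 4 (0.025 per tail) gives 73.0%. If those lost are non-responders, both rates rise (0.04/0.9 = 4.44%, 0.32/0.9 = 35.56%) and it gives 80.6%, against 80.3% at the start. Counting 10% as non-responders (3.6% against 28.8%, 25 against 50) gives 72.5%, so that remedy restores no power.

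**Conclusion.** The labelling rule is a real inconsistency and worth correcting. For endpoints measured only at baseline and Week 12, it combines with the absence of imputation to make the readable Week 12 analyses in effect observed-case. This holds within the FAS for subgroup MRI-PDFF and MRE, and within the safety data for the ECG shift table.

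A reader might go further and conclude that the whole FAS efficacy analysis is restricted to completers. The documents do not show that. SAP 6.1 and 6.2.1 are redacted and may define a denominator or a missing-data rule for the main analysis. Weeks 1, 4 and 8 still include subjects who drop out later. Subjects off drug with a nominal Week 12 scan still count.

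The size depends on an unknown ET rate and on who stops. With the assumed 5 of 50, the 20 mg rate moves from 32.0% to anywhere between 24.4% and 35.6%. The direction cannot be known beforehand, which is the reason to fix the rule in advance. Efficacy is exploratory, so this is an inexpensive improvement and not a threat to the trial's primary objective.

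**What to change.** 1. In SAP 3.8.2, count an ET value as Week 12 when no other Week 12 value exists and it falls on or after Day 71, the limit already used in Table 3-1. Keep the separate ET display.
2. Raise the Week 12 lower limit in Table 3-4 from Day 2 to Day 71. Apply the same limit to Table 3-5, or justify Day 30.
3. Add a sensitivity analysis of MRI-PDFF and MRE response that uses the ET scan when there is no Week 12 scan and counts subjects with neither as non-responders. State the denominator of the response proportions in SAP 6.3.

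The cost is a few lines of SAP wording and one sensitivity table on data already collected. The downside is that some ET scans reflect less than 12 weeks of drug. The Day 71 limit bounds this in item 1. In item 3, which uses ET scans of any date, it should be noted when the results are read.

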4. SUBJECT DISPOSITION

4.1. Subject Enrollment and Disposition

A summary of subject enrollment will be provided for each investigator by treatment group and overall. For each column, the denominator for the percentage calculation will be the total number of subjects analyzed for that column.

A similar enrollment table will be provided by randomization stratum. The denominator for the percentage of subjects in the stratum will be the total number of randomized subjects in the All Randomized Analysis Set. If there are discrepancies in the value used for stratification assignment between the IXRS and the clinical database, including CRF and laboratory data, the value collected in the clinical database will be used for the summary. A listing of subjects with discrepancies in the value used for stratification assignment between the IXRS and the clinical database at the time of data finalization will be provided.

The randomization schedule used for the study will be provided as an appendix to the CSR.

A summary of subject disposition will be provided by treatment group and overall. This summary will present the number of subjects randomized, and the number and percentage of subjects in each of the categories listed below.

- Safety Analysis Set
- Full Analysis Set
- PK Analysis Set
- CCI [REDACTED]
- Completed study drug
- Did not complete study drug, with reasons for premature discontinuation of study drug
- Completed study
- Did not complete the study, with reasons for premature discontinuation of study

In addition, a flowchart will be provided to depict the disposition.

The following by-subject listings will be provided by subject identification (ID) number in ascending order to support the above summary tables:

- Reasons for premature study drug or study discontinuation
- Reasons for screen failure (will be provided by screening ID number in ascending order)
- Lot number and kit ID

4.2. Extent of Study Drug Exposure and Adherence

Extent of exposure to study drug will be examined by assessing the total duration of exposure to study drug and the level of adherence to the study drug specified in the protocol.

4.2.1. Duration of Exposure to Study Drug

Total duration of exposure to study drug will be defined as last dosing date minus first dosing date plus 1, regardless of any temporary interruptions in study drug administration, and will be expressed in weeks using up to 1 decimal place (e.g., 4.5 weeks). If the last study drug dosing date is missing, the latest date among the study drug end date, clinical visit date, laboratory sample collection date, and vital signs assessment date that occurred during the on-treatment period will be used.

Total duration of exposure to study drug (weeks) = (last dose date - first dose date + 1)/7

The total duration of exposure to study drug will be summarized using descriptive statistics (sample size, mean, SD, median, Q1, Q3, minimum, and maximum) and using the number (ie, cumulative counts) and percentage of subjects exposed through the following time points: 1 day, 1 week, 4 weeks, 8 weeks, and 12 weeks.

Summaries will be provided by treatment group for the Safety Analysis Set.

No formal statistical testing is planned.

4.2.2. Adherence to Study Drug

The total number of doses administered will be summarized using descriptive statistics.

The presumed total number of doses administered to a subject will be determined by the data collected on the drug accountability CRF using the following formula:

Total Number of Tablets Administered =

$$\left(\sum \text{No. of Tablets Dispensed} \right) - \left(\sum \text{No. of Tablets Returned} \right)$$

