### **5.2.2. Packaging and Labeling**

GS-0976 capsules and PTM GS-0976 are packaged in white, high density polyethylene (HDPE) bottles. Each bottle contains 30 capsules. Each bottle is enclosed with a white, continuous thread, child-resistant polypropylene screw cap with an induction-sealed and aluminum-faced liner.

Study drugs to be distributed to centers in the US shall be labeled to meet applicable requirements of the United States Food and Drug Administration (FDA) and/or other local regulations.

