## **5.3. Dosage and Administration of GS-0976/PTM GS-0976**

GS-0976 capsules will be provided by Gilead Sciences. Subjects will take 4 capsules of GS-0976 (5 mg, 5 mg-PTM, 10 mg, or 10 mg-PTM) once daily at approximately the same time each morning. Study drugs should be swallowed whole with water and may be taken with or without food. A dose will be considered missed if the subject cannot take the dose within 12 hours of their regular dosing time. If a subject misses a dose, the subject should take their

next dose at the regular dosing time. Study drug dosing and administration will occur as follows, based on treatment group randomization:

- Treatment Group A: GS-0976 5 mg (1 x 5 mg capsule + 1 x 5 mg-PTM capsule + 2 x 10 mg-PTM capsules) administered orally once daily;
- Treatment Group B: GS-0976 20 mg (2 x 10 mg capsules + 2 x 5 mg-PTM capsules) administered orally once daily;
- Treatment Group C: GS-0976 Placebo (2 x 5 mg-PTM capsules + 2 x 10 mg-PTM capsules) administered orally once daily.

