4.2.2.1. Prescribed Adherence

The level of prescribed adherence to each type of the study will be determined by the total amount of study drug administered relative to the total amount of study drug specified by the protocol for a subject who completes treatment in the study.

The level of prescribed adherence will be expressed as a percentage using the following formula:

$$\text{Prescribed Adherence (\%)} = \left(\frac{\text{Total Amount of Study Drug Administered}}{\text{Total Amount of Study Drug Specified by Protocol}} \right) \times 100$$

Note: If calculated adherence is greater than 100%, the result will be set to 100%.

Descriptive statistics for the level of prescribed adherence with the number and percentage of subjects belonging to adherence categories (< 75%, ≥ 75 to < 90%, and $\geq 90\%$) will be provided for each study drug by treatment group for the Safety Analysis Set.

No formal statistical testing is planned.

By-subject listings of study drug administration and drug accountability will be provided separately by subject ID number (in ascending order) and visit (in chronological order).

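### SAP 4.2.2 counts capsules as doses and unreturned capsules as taken, and the 100% cap hides the resulting excess in the adherence table

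*SAP*

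**What the plan says.** SAP 4.2.2 announces that "The total number of doses administered will be summarized using descriptive statistics" and that "The presumed total number of doses administered to a subject will be determined by the data collected on the drug accountability CRF". The formula that follows has on its left side "Total Number of Tablets Administered" and on its right the sum dispensed minus the sum returned. It has no step from units to doses and no rule for drug that is not brought back.

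The protocol describes a capsule product. Under Protocol 5.3, "Subjects will take 4 capsules of GS-0976 (5 mg, 5 mg-PTM, 10 mg, or 10 mg-PTM) once daily"; the 5 mg regimen, for example, is "1 x 5 mg capsule + 1 x 5 mg-PTM capsule + 2 x 10 mg-PTM capsules". Under Protocol 5.2.2, "Each bottle contains 30 capsules". Protocol 5.5 requires all bottles to be returned to the site.

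SAP 4.2.2.1 defines prescribed adherence as the amount administered divided by the amount specified for a subject who completes treatment. It groups the result as below 75%, 75 to below 90%, and 90% or more. It also sets a ceiling: "If calculated adherence is greater than 100%, the result will be set to 100" (percent). It speaks of adherence by type, in a sentence where a word seems to be missing, and of results by study drug. It does not say whether that means each kind of capsule or the four-capsule regimen.

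**The concern.** Three things need attention.

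- **Units.** The quantity to be reported is doses, but the formula that determines it yields capsules.
- **Unreturned drug.** A bottle that never comes back subtracts nothing, so its contents count as swallowed. The missing-data rules listed in SAP 3.6.1 do not cover accountability data. The error can only raise apparent adherence, and the cap then removes the value above 100% that would have revealed it.
- **Level of calculation.** Each active regimen mixes active and placebo capsules, so a figure over all capsules and a figure per capsule type can differ widely.

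The primary objective is safety and tolerability, which has to be read against how much drug was taken. Duration of exposure in SAP 4.2.1 ignores temporary interruptions, so adherence is the planned summary that speaks to intake.

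**Working it through.** **Inputs**

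- Capsules per daily dose: 4 in every group (Protocol 5.3). Check: 5 mg group 1 + 1 + 2 = 4; 20 mg group 2 + 2 = 4; placebo 2 + 2 = 4.
- Active capsules per day: 1 (5 mg), 2 (20 mg), 0 (placebo).
- Duration: 12 weeks = 84 daily doses (Protocol 3.2).
- Dispensing visits: Day 1, Week 4, Week 8 (Protocol Appendix 2).
- Bottle size: 30 capsules. Bottles per visit are not stated. Assumption: 4 bottles, so 120 capsules per visit and 360 in all.

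The adherence section states no dose total, so there is no figure of the plan's own to reproduce beyond the four capsules per day.

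**1. Dose count.** A full course is 84 × 4 = 336 capsules. The formula returns 336; the number of doses is 336/4 = 84. The ratio is 4. The percentage does not change: 63 of 84 doses is 75%, and 252 of 336 capsules is also 75%.

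**2. Unreturned supply.** Adherence = (dispensed − returned)/336, capped at 100%.

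| Subject | Formula | Shown as | Actually taken |
|---|---|---|---|
| Takes two supplies in full (56 × 4 = 224), returns 16, neither takes nor returns the third | (360 − 16)/336 = 102% | 100% | 224/336 = 67% |
| Receives all three supplies, returns nothing | 360/336 = 107% | 100% | unknown |
| Receives Day 1 and Week 4 supplies only, returns nothing | 240/336 = 71.4% | 71.4% | unknown |
| Receives Day 1 supply only, returns nothing | 120/336 = 35.7% | 35.7% | unknown |

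The first row does not depend much on the pack assumption. If each supply were exactly 28 × 4 = 112 capsules with nothing left over, the score would be (224 + 112)/336 = 100%, still against 67%. Calculating per capsule type does not cure this: for one capsule position, three unreturned 30-capsule bottles give 90/84 = 107%, again shown as 100%.

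**3. Level of calculation, if pooled over all capsules.** A subject who takes every placebo capsule, takes no active capsule and returns the active ones scores:

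- 5 mg group: (336 − 84)/336 = 75%, in the middle category;
- 20 mg group: (336 − 168)/336 = 50%, in the lowest category.

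To stay at 90% or more, at most 33 capsules can be missed (10% of 336 is 33.6). Active intake could then be as low as (84 − 33)/84 = 61% in the 5 mg group and (168 − 33)/168 = 80% in the 20 mg group. Calculated per type, the subject who takes no active capsule scores 0% on active drug in either group.

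**The case against.** The best defence is that this is loose labelling with little consequence. The formula's output is named as tablets, 336 is the correct number of units, and the percentage is untouched. That stands for the percentage. It does not rescue the dose count, because the SAP says the formula determines the number of doses.

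On unreturned drug, the protocol requires all bottles back, schedules pill counts at Weeks 1, 4, 8 and 12, and the SAP itself calls the count presumed. The full-course denominator also protects against the obvious case: on the assumed supply, subjects lost before the Week 8 dispensing stay below 75%, as the table shows. This stands, and it confines the capped result mainly to subjects who received the Week 8 supply. It does not supply a rule for those subjects.

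Adherence is also not the only check on intake. The SAP summarises exposure duration, lists administration, accountability and kit identifiers by subject, and names nonadherence as an example of an important deviation; PK samples are taken at each on-treatment visit. This limits the impact.

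Three stronger readings are tempting, and the documents do not support them:

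- **That active and placebo capsules are pooled.** SAP 4.2.2.1 refers to types and to each study drug, so separation may be intended. The level is undefined, no more.
- **That pooling lets a subject who took no active drug be reported as adherent.** Pooling alone gives at most 75% or 50%, and the SAP defines no adherent class.
- **That the cap hides overdose.** Protocol 7.6.1 does not let an unexplained accountability discrepancy establish overdose by itself, and overdoses are reported through the special-situations route.

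**Conclusion.** The point holds in a limited form. Followed as written, SAP 4.2.2 overstates the number of doses fourfold (336 against 84 for a full course). It also biases adherence upward whenever capsules are not returned: true intake of 67% can appear as 100%. The first result rests only on figures in the protocol. The second rests on an assumed 120 capsules per dispensing, though any supply sufficient for 28 days gives the same capped value in that example. How often bottles go unreturned cannot be judged from the documents. Whether adherence is pooled or per capsule type is an ambiguity to settle. The summaries are descriptive and no visible analysis set uses them, so this affects how exposure is reported and does not alter the planned safety or efficacy comparisons. It is still worth correcting, because the error from unreturned drug runs in one direction only.

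**What to change.** In SAP 4.2.2 and 4.2.2.1:

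1. Replace tablets with capsules, and divide capsules by 4 to obtain doses. Use capsules in both terms of the adherence ratio.
2. State that adherence is calculated per capsule type (5 mg, 10 mg and each matching placebo). The final analysis follows unblinding (SAP 2.2), and SAP 4.1 already lists kit identifiers.
3. Treat capsules in unreturned bottles as unknown, not taken. Flag the affected subjects and show adherence with and without them.
4. Report the number of subjects above 100% before the cap is applied.

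The cost is SAP wording and minor programming. Protocol 5.5 has sites record bottle numbers dispensed and quantities returned; the accountability CRF is not among the documents, so whether it holds counts by bottle should be confirmed. The downside is that some subjects will have unknown adherence and the reported level may be slightly lower.
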